10.2 Power Calculation

Based on an accrual period of 3 years and minimum follow-up of 12 months major events will be recorded for a minimum of 12 months and a maximum of 4 years. Major events over this duration can easily be incorporated into the Win Ratio analysis to maximise power and more appropriately account for the impact of more serious clinical outcomes. Calculations for the unmatched pairs Win Ratio analysis are not well established at present and require many underlying assumptions. Hence, we have first calculated sample size using a conventional approach (incorporating modest power).

In the PROTECT II trial the composite endpoint comparable to that proposed in CHIP was 40% at 30 days and 50% at 90 days. Assuming a more conservative event rate of 50% at 12 months in the control arm a trial of 250 (125 in each group) would have well in excess of 80% power to detect a hazard ratio of 0.62 requiring approximately 150 first events using all follow-up time (which, at these event rates, represents a risk ratio of 0.70 at 12 months) allowing for 5% losses. Whilst this rate may appear to be high at first, it is based on published data from high risk intervention. Given the established superior statistical power of a Win Ratio analysis and other secondary analyses accounting for repeated events in trials with low crossovers, a sample size of 250 patients was expected to provide good power to detect important clinical differences between the treatment groups. Crossovers will be evaluated throughout the trial.

10.2.1 Sample size extension

Due to successful recruitment, the opportunity arose for the investigators to extend recruitment and increase the sample size to 300 participants. The decision to design and conduct CHIP-BCIS was largely influenced by the position taken by NICE in 2018, when it was felt that there was insufficient evidence to support routine use of this strategy in the NHS and that more research on its safety and efficacy was a priority. Whilst a 30% relative risk reduction would enable NICE to issue clear guidelines on the use of LV unloading in the UK, increasing the sample size would allow an even smaller treatment effect to be assessed and hence provide NICE (as well as other healthcare systems and international guideline committees) with more definitive evidence on which to base their recommendations.

A further advantage of extending the accrual period is that the follow-up period of the 250 patients first recruited to the trial would be extended by the duration of the additional recruitment period. In total, we estimate that the proposed changes would lead to an increase in total follow-up by approximately 140 patient-years, which would allow capture of more clinical events, hence increasing statistical power. Given that the additional events captured will be those occurring later following randomisation, this will also potentially lead to more pairwise comparisons in the primary (win ratio) analysis being determined by components higher-up the hierarchy than peri-procedural MI, thereby also increasing clinical impact.

The TSC initially considered an increase in sample size in July 2023, subject to satisfactory progress in recruitment over the following 6 months. Accordingly, the TSC reviewed recruitment rates again in February 2024 and recommended an increase in the sample size to 300. An application to the funder was made in March 2024 and approved in May 2024.

10.2.2 Secondary Endpoints

Individual components of the hierarchical combined primary endpoint as well as repeated occurrences of these events, health-related quality of life, New York Heart Association (NYHA) functional class, completeness of revascularisation and resource utilisation at 90 days, yearly and at the end of the trial. The combined outcome and individual components will also be analysed using Cox proportional hazard models for the time-to-first event over the follow-up period. Other analyses such as sensitivity and per-protocol analyses will be detailed in the statistical analysis plan.

10.3 1-year feasibility review

A review of recruitment and pooled event rates was performed approximately one year after the first patient was recruited to inform the feasibility of completing the trial within the initial projected period. As the number of patients randomised was still relatively small and length of follow-up short, it was felt that the expected number of events at this stage of the trial was too low for meaningful assessment. Recruitment and the pooled event rate will continue to be monitored as the trial progresses.

An independent DMC has been established and a separate DMC charter developed which includes details of the meeting schedule and stopping guidelines. The DMC is expected to meet at least annually.

11. Screening

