7.4 Endpoint Definitions

Disabling Stroke	Stroke is defined as an acute episode of focal or global neurological dysfunction caused by brain, spinal cord, or retinal vascular injury as a result of hemorrhage or infarction, resulting in persistent moderate disability (modified Rankin Scale ≥ 3) at the time of discharge from the acute hospital admission.
Acute Myocardial Infarction	
1. Spontaneous MI (>48 hours after PCI/CABG) Detection of a rise and/or fall of cardiac Troponin I or T, with at least one value higher than the 99th percentile upper reference limit (URL) AND symptoms consistent with ischaemia OR dynamic electrocardiogram (ECG) changes (including ≥ 1mm ST elevation or ST depression, new left bundle branch block (LBBB) or >3mm T-wave inversion) OR imaging evidence of new loss of viable myocardium or new regional wall motion abnormality in a pattern consistent with an ischaemic aetiology.
 
2. Peri-procedural MI (<48 hours after PCI/CABG) Following PCI: Detection of a rise in cardiac troponin I or T, with the threshold of significance determined by the pre-procedure baseline value.
 
Baseline \leqURL: At least one value higher than five times the URL
 
Baseline $>$ URL and stable or falling: At least one value higher than 5xURL above the baseline value or 20% above the baseline value, whichever is greater.
 
Baseline $>$ URL and rising: At least one value higher than 5xURL above the predicted value* or 20% above the predicted value, whichever is greater.
 
*the predicted value will be calculated via linear extrapolation of the trend from at least two troponin values taken within 48 hours before the procedure.
 
Following CABG: As for PCI, but with a threshold of 10xURL. In addition to classifying patients dichotomously as having suffered a periprocedural MI or not, baseline and peak troponin I or T values measured within 24 hours of a procedure will be recorded. This will provide a continuous measure for adjudication of ties in patients reaching the periprocedural myocardial infarction endpoint within the Win Ratio.
 
Absolute values of troponin, ECGs and supporting information will be collected for all patients who experience a periprocedural MI, so that sensitivity analyses based on alternative definitions can be explored.

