10.1 Win Ratio

The analysis will be undertaken by use of the Win Ratio, an increasingly recognised approach to allow for the hierarchy of events as well incorporating repeat events such as myocardial infarctions or hospitalisations[12,13]. The Win Ratio is the ratio of “winners” on the intervention compared to “losers” thus a value above 1 indicated a benefit of the intervention. Confidence intervals can be calculated as well as p-values and the process extended for repeat component events.

The combined hierarchical endpoint is all-cause death, stroke, spontaneous myocardial infarction (MI), cardiovascular hospitalisation and peri-procedural MI. The outcome hierarchy is as follows:

- (1) All-cause death
- (2) Stroke (defined as disabling stroke thus not including transient ischaemic attacks)
- (3) Spontaneous MI
- (4) Cardiovascular hospitalisation
- (5) Peri-procedural MI

The Win Ratio will use an unmatched pairs approach with each individual in the intervention arm compared to each individual in the standard care arm, using the stepwise sequence below, to adjudicate a winner/loser or declare a tie. For each comparison the common follow-up is defined in which follow-up is censored at the duration of the shorter follow-up interval. For example, if one patient has been followed for 1 year and the second patient for 2 years then for that specific comparison events up to one year will be considered.

- Step 1: Compare all-cause mortality – if one has died, the survivor is the winner, if both have died, the patient who survives longer is the winner and if neither has died (or both die at the same interval from randomisation) proceed to step 2
- Step 2: Compare time to occurrence of disabling stroke, as above. If no winner, proceed to step 3.
- Step 3: Compare time to occurrence of spontaneous MI (as per Universal Definition) as above. If no winner, proceed to step 4.
- Step 4: Compare the number of cardiovascular hospitalisations (as defined in the trial protocol). The patient with the least number of hospitalisations occurring within the common follow-up period is the winner. If the same number of hospitalisations have occurred, the patient who survives longer before the first hospitalisation is the winner. If neither have had a cardiovascular hospitalisation in this period, proceed to step 5.

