- Step 5: Compare periprocedural MI. If only one has had a periprocedural MI, the patient who does not have a MI is the winner. If both have had a periprocedural MI, the patient with the smaller infarct size, as measured by peak Troponin level (expressed as a multiple of the 99th centile, to allow comparison of different Troponin assays) is the winner, unless the difference in increase in troponin level between patients is $\leq 5x$ the URL, in which case a tied will be declared. If neither patient has had a periprocedural MI, the stepwise comparison is concluded and the result declared a tie.

This approach is designed to optimise the impact of individual components of a composite endpoint, by allocating greater weight to more important events, increasing the range of events considered and allowing capture of recurrent events. The requirement for a $\geq 5x$ URL difference in troponin level in determining wins based upon peri-procedural MI is designed to ensure a clinically meaningful

difference in all declared wins. When analyses of recurrent events has been applied to simulated data and major contemporary heart failure trials precision has been shown to improve when treatment discontinuation is low following the first event[14]. Since the intervention is high-risk PCI and not drug therapy crossover rates are expected to be negligible allowing a smaller sample size whilst maintaining power. In contrast, a traditional composite endpoint trial using time to first event analysis weights each event equally and only incorporates the first event hence many more serious outcomes, such as death, may not included and no account is taken of later events. The sample size using such an approach would require a larger treatment difference to be detected (as illustrated below) or require a prohibitively large and expensive trial and would not be able to complete recruitment in a reasonable timeframe.

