14.2 Vascular Core Lab

Both pre-randomisation and trial procedure coronary angiogram, coronary angioplasty images, intracoronary imaging and peripheral vascular imaging will be transferred to a vascular core laboratory. Each participant's pre-randomisation BCIS JS and PCI procedural success will be independently validated by the core laboratory. The core laboratory will calculate a number of other scores reflecting the anatomic complexity of coronary disease, the extent of effective revascularisation and the complexity of CTO lesions.

This data will be used to conduct a number of sub-analyses to identify predictors of benefit for the primary and secondary outcomes. The core laboratory will subsequently provide the relevant data to the Sponsor and CTU at the London School of Hygiene & Tropical Medicine for analysis against the data held in the eCRF.

15. Randomisation

Potential patients will be reviewed by the Principal Investigator before randomisation with all available tests/notes to confirm eligibility.

Once the eligibility of a patient is confirmed by the trial coordinators and written informed consent obtained, randomisation will be carried out via an online web-based system. Randomisation of the treatment assignment will be stratified by centre using randomly permuted blocks of varying size, with 1:1 allocation between the LV-unloading and non-LV unloading arms.

There is no time limit from randomisation to PCI. However, it is recommended that index PCI be carried out as close as possible to randomisation to minimise the incidence of events prior to the assigned treatment. Clinical events that occur after randomisation but before planned PCI will be attributed to the assigned treatment on an intention-to-treat basis.

16. Percutaneous Coronary Intervention

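### Peri-procedural MI falls under the Cox time-to-first-event plan, but its time from randomisation is essentially the procedure date, so its hazard ratio would favour the later-treated arm if waits differ

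*Protocol*

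**What the plan says.** Section 10.2.2 fixes the secondary analysis: the combined outcome and "individual components will also be analysed using Cox proportional hazard models for the time-to-first event over the follow-up period". It excepts no component. It leaves sensitivity and per-protocol analyses to the SAP, but the choice of model is made in the protocol itself.

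Section 10.1 gives peri-procedural MI its own level in the hierarchy ("5) Peri-procedural MI"), separate from spontaneous MI at level 3. Section 7.4 limits when it can happen: "Peri-procedural MI (<48 hours after PCI/CABG".

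On timing, section 15 states: "There is no time limit from randomisation to PCI". It then adds that "it is recommended that index PCI be carried out as close as possible to randomisation", which is advice and not a rule. Section 4 describes the design as open-label.

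The primary analysis handles the same event without using time. At step 5 of section 10.1, "If only one has had a periprocedural MI, the patient who does not have a MI is the winner"; if both patients have had one, peak troponin decides.

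**The concern.** A Cox model compares the order in which events occur. For death, stroke, spontaneous MI and hospitalisation, that order carries information about the treatment. For peri-procedural MI it carries almost none, because the event time is the wait for the procedure plus at most two days. A patient who infarcts at a procedure on day 40 has not done better than one who infarcts at a procedure on day 10.

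If the two arms were treated at different times after randomisation, the later arm would gain a hazard ratio below 1 even with identical infarct risk per procedure. The estimate for this component could then be misread as fewer infarctions. In weaker form the same would apply to the time-to-first-event version of the combined endpoint, which section 7.2 lists first among the major secondary endpoints.

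**Working it through.** **1. The plan's own figures.** The protocol gives no number for this point. Its nearest figures, in section 10.2, are more than 80% power at a hazard ratio of 0.62 with about 150 first events, and a 12-month risk ratio of 0.70. Both reproduce (two-sided 5% is assumed, since no level is stated for the main trial):

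- Power (Schoenfeld) = Φ(|ln 0.62| × √150 / 2 − 1.96) = Φ(2.93 − 1.96) = 83.3%.
- Risk ratio = (1 − 0.5^0.62) / 0.5 = 0.699.

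Neither figure is disputed. The 0.62 is a yardstick for the sizes below.

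**2. Time origin.** Section 10.2.2 does not name the origin for the Cox models. Randomisation is inferred from two places: the win ratio treats deaths as tied "or both die at the same interval from randomisation", and section 15 says "Clinical events that occur after randomisation but before planned PCI will be attributed to the assigned treatment on an intention-to-treat basis".

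**3. Largest effect that ordering alone can produce.** Take equal arms, the same infarct risk p in both, no deaths or censoring before PCI, and every procedure in the early arm before any in the late arm. With θ the hazard ratio (late v early), setting the Cox score to zero gives

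θ ln[(1+θ)/(1+θ−p)] = ((1−p)/θ) ln[(1+θ−p)/((1−p)(1+θ))],

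which is solved by θ = √(1−p). Hence √0.9 = 0.95, √0.8 = 0.89, √0.7 = 0.84, √0.6 = 0.77 and √0.5 = 0.71. The size depends on the infarct risk and on how far the two distributions of waits are separated.

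**4. Simulation under no true effect.** From the protocol: 150 per arm (300 in total, 1:1) and follow-up of 1 to 4 years. Assumed, because the protocol gives neither: the waits and the MI risk. Mortality of 15% per year is also assumed. Each setting had 2,000 runs, and rejection is two-sided at 5%.

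| MI risk | Waits 14 v 28 days, exponential: HR (rejection) | 14 v 42 days, exponential | 14±7 v 42±7 days, no overlap |
|---|---|---|---|
| 10% | 0.97 (5.9%) | 0.97 (5.1%) | 0.95 (5.3%) |
| 20% | 0.95 (5.3%) | 0.93 (5.2%) | 0.89 (7.9%) |
| 30% | 0.93 (5.8%) | 0.91 (6.9%) | 0.83 (16.1%) |
| 40% | 0.91 (8.7%) | 0.86 (12.1%) | 0.76 (31.2%) |

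With equal waits (14 v 14 days) the hazard ratio is 0.99-1.00 and rejection is 4.5-5.4%. The no-overlap column agrees with √(1−p), apart from the small effect of deaths.

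**5. Range used for the conclusion.** For exponential waits with means from 7 v 14 up to 14 v 45 days, the hazard ratio for peri-procedural MI is about 0.96-0.98 at 10% risk, 0.93-0.96 at 20%, 0.89-0.93 at 30% and 0.86-0.92 at 40%. Rejection is 5-6% at 10-20% risk and 6-13% at 30-40%.

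**6. Composite.** Other events dilute the effect, and the hazard ratio is 0.91-1.00 over the same range. For a composite of death and peri-procedural MI at 30% risk it is 0.94 (14 v 42 days, exponential) and 0.90 (no overlap).

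**7. Binary comparison.** Comparing proportions in all randomised patients keeps rejection at 4.2-5.6% whatever the difference in waits.

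**The case against.** The strongest reply is that the problem needs unequal waits and nothing in the protocol shows them. Section 15 recommends early PCI. Section 16.1 strongly recommends CT angiography of the peripheral vessels before enrolment in all patients, and places the access and closure plan for difficult cases before randomisation. Access planning is therefore not a good reason to expect the unloading arm to wait longer. A reader might infer that one arm is scheduled later, or that the design tilts towards unloading. The documents support neither. Open-label booking makes a difference possible, and the arm-specific rules in sections 16.5 (staged procedures) and 16.7 (when the assigned strategy cannot be followed) could move procedure dates. None of this says which way, or by how much.

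The size also depends on the MI risk. The only 40% in the protocol is the 30-day rate of a whole composite in an earlier randomised trial (section 10.2), not a peri-procedural MI rate. At 10-20% risk the effect is slight.

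Two further points stand in part. Section 7.1 names myocardial infarction as a single component, so a separate Cox model for peri-procedural MI rests on the five-level list in section 10.1. And because section 7.4 covers any PCI or CABG, a later staged or unplanned procedure can produce the event, so time and censoring are not wholly irrelevant to it.

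What survives is narrower. The protocol commits, without exception, to a model that does not suit this event, while its own primary analysis compares the event without time.

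**Conclusion.** The point holds as a conditional weakness in one stated secondary analysis. If waits from randomisation to PCI differ by arm, the Cox hazard ratio for peri-procedural MI favours whichever arm is treated later, and if they do not differ there is no bias. Under the assumed waits the shift is small at 10-20% MI risk (hazard ratio 0.93-0.98). It becomes material only at about 30-40% risk with clearly unequal waits (0.86-0.93). All of these are far from the design effect of 0.62. The conclusion rests on randomisation as the time origin, which is inferred, and on waits and risks that the protocol does not give.

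It would be wrong to read this as a threat to the primary result through peri-procedural MI, since step 5 of the win ratio ignores its timing. It would be equally wrong to read it as evidence that either arm does wait longer. This is a minor, inexpensive improvement.

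**What to change.** In section 10.2.2, state that peri-procedural MI will be analysed as a binary outcome in all randomised patients, with a risk ratio and a risk difference. Keep the Cox models for death, stroke, spontaneous MI and cardiovascular hospitalisation. Report the time from randomisation to PCI by arm, so that readers can see whether the condition for bias arises. Add a 12-month risk ratio as a check on the time-to-first-event composite.

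The cost is a sentence or two in the protocol and a little extra analysis, with no new data. It is best settled before unblinding. The one loss is that the timing of rare later peri-procedural MIs, after staged or unplanned procedures, is no longer used.

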11.1 Screening Population

All patients undergoing PCI should be screened for eligibility at the time of listing. They may come from the following sources:

- Patients referred to the Heart Team for consideration of revascularisation
- Patients seen in outpatient clinics for consideration of PCI
- Patients referred for advanced imaging to plan complex revascularisation
- Patients currently admitted with acute coronary syndromes or acute heart failure, either at the site or planned for transfer from a referring centre.
- Following coronary angiography in patients who are known to have poor resting LV function
- Participant Identification Centres (PICs)

11.2 Screening Log

Detailed screening logs of all patients with extensive CAD and EF $\leq 35\%$ considered for the trial will be completed at sites. Details of all patients who undergo pLVAD supported high-risk PCI at the site will also be collected at the same time as the screening log.

The CTU will collect screening logs from the recruiting sites each month. Once recruitment is established, and if the TSC agrees it is appropriate, screening information may be collected less frequently.

12. Assessment of LVEF

12.1 Qualifying Ejection Fraction

To determine eligibility for the trial, LVEF can be determined by the following modalities:

- Transthoracic echocardiogram (TTE) (Simpson's biplane on 2D or 3D echocardiography)
- The resting stage of a stress echocardiogram
- Cardiac MRI

The qualifying assessment **must** have been carried out less than 1 year before randomisation. Estimation of LVEF and adjudication of eligibility for enrolment in will be done by each participating centre, using locally agreed protocols.

13. Viability Testing

Viability testing is not mandated. However, as per current international guidelines, formal testing for myocardial viability is strongly recommended for all patients undergoing PCI with severely impaired left ventricular function.

14. Core Laboratories

14.1 Imaging Core Lab

All trial echocardiograms should be performed in accordance with the minimum standard set out by the British Society of Echocardiography. Viability studies should be carried out in accordance with the relevant national and international society guidelines, dependent on modality.

If the qualifying echocardiogram study was performed less than 6 months before randomisation, this study can also be submitted to the core lab to calculate baseline LVEF. If the qualifying echocardiogram was done more than 6 months before randomisation, or the qualifying LVEF was assessed using MRI, a further transthoracic echocardiogram should be carried out soon after randomisation and this study submitted to the core lab to calculate baseline LVEF. Any viability study performed in the 12 months prior to randomisation should be submitted to the core laboratory.

Baseline echocardiograms and viability studies will be anonymised and submitted to an imaging core laboratory which will determine LV volumes and EF using a Simpson's biplane method and segmental myocardial viability and (where available) ischaemia from the viability study. The core laboratory will be blinded to treatment assignment as well as to the timing of the studies in relation to randomisation.

The core laboratory will subsequently provide the relevant data to the Sponsor and CTU at the London School of Hygiene & Tropical Medicine for analysis against the data held in the eCRF.

